**VERSION HISTORY**

|            |  |
|------------|--|
| 2018-08-27 | NHLBI Cardiovascular Branch Review   |
| 2019-02-06 | Interactive FDA IDE review   |
| 2019-02-27 | Change to single IRB of record   |
| 2019-05-12 | Amendment A: MitraClip Arm, increase in sample size, other study clarifications           |
| 2019-06-27 | Amendment B: Clarifications of, secondary endpoint, ADE, reporting, consent                      |
| 2019-09-06 | Amendment C: Additional CT scan, remove NIH as enrolling site                                    |
| 2019-10-21 | Amendment D: Screening consent, minor cleanup  |
| 2020-02-18 | Amendment E: Additional sites and optional non-invasive tests                                    |
| 2020-07-09 | Amendment F: Change selection criteria   |
| 2021-06-14 | Amendment G: Add long term FU adverse event recording and reporting criteria; Additional CT scan |

**ESTIMATED DURATION OF STUDY:**

[6 years]

**ESTIMATED COMPLETION DATE OF STUDY:**

December 31, 2024

**SUBJECTS OF STUDY AND SITES:**

| Subjects                   | Sex         | Age range | Sites   |
|----------------------------|-------------|-----------|---------|
| 60 screened
30 enrolled | Men & Women | ≥21 years | Up to 6 |

## ABBREVIATIONS

|       |  |
|-------|--|
| ADE   | Adverse Device Effect  |
| CIED  | Cardiac implanted electronic device  |
| CMR   | Cardiovascular magnetic resonance imaging                                  |
| CMS   | Centers for Medicare and Medicaid Services                                 |
| CRT   | Cardiac resynchronization therapy  |
| CT    | Computed tomography  |
| CTP   | CMS Clinical Trial Policy (CTP).   |
| DIR   | Division of intramural research  |
| EFS   | FDA Early Feasibility Study under Investigational Device Exemption license |
| HFpEF | Heart failure with preserved ejection fraction                             |
| HFrEF | Heart failure with reduced ejection fraction                               |
| ICD   | Implanted cardioverter defibrillator                                       |
| IEC   | Institutional Ethics Committee   |
| IRB   | Institutional Review Board   |
| MVARC | Mitral valve academic research consortium (criteria)                       |
| MR    | Mitral valve regurgitation   |
| MS    | Mitral valve stenosis  |
| SAE   | Serious Adverse Event  |
| SADE  | Serious Adverse Device Effect  |
| SEC   | Study eligibility committee  |
| TEE   | Transesophageal echocardiography   |
| TMCA  | Transcatheter Mitral Cerclage Annuloplasty                                 |
| TTE   | Transthoracic echocardiography   |
| UADE  | Unanticipated Adverse Device Effect  |
| UP    | Unanticipated Problem  |

## 0.0 PUBLIC PRÉCIS

This research protocol tests a new technique and devices that we have developed to treat functional mitral valve regurgitation, called transcatheter mitral valve cerclage annuloplasty, otherwise known as “cerclage.” Functional mitral valve regurgitation is a condition caused by damaged heart muscle involving the left ventricle which results in mitral valve leakage. This leakage causes heart failure (breathlessness and lack of energy especially when walking or exercising, and hospital admissions for fluid buildup).

This is an early feasibility study (EFS) evaluation of special devices, permanently implanted in the heart, to perform mitral cerclage annuloplasty. Mitral cerclage annuloplasty is a catheter procedure performed under X-ray and ultrasound guidance without surgery. The cerclage devices compress the mitral valve like a purse-string. The cerclage device has a special feature that prevents a coronary artery from getting squeezed as part of this purse-string.

The protocol has been changed to allow patients who have mitral valve regurgitation despite prior *Mitra-Clip* treatment. The protocol has been changed to allow patients who have symptomatic heart failure and mild mitral regurgitation.

## 1.0 OBJECTIVE

The original objective of this protocol is to evaluate the feasibility and safety of Transcatheter Mitral Cerclage Annuloplasty to treat severe functional mitral valve regurgitation in patients with NYHA class II, III or IV heart failure symptoms despite optimal medical therapy.

**In Amendment F**, the objective of this protocol is changed to evaluate the feasibility and safety of Transcatheter Mitral Cerclage Annuloplasty to treat symptomatic heart failure accompanied by mitral valve regurgitation despite optimal medical therapy. New subjects may have less severe mitral valve regurgitation compared with the first 10 subjects.

## 2.0 BACKGROUND

Functional mitral regurgitation (also known as secondary mitral regurgitation) is a common manifestation of left ventricular dysfunction. Ventricular dysfunction leads to dilation, which in turn leads to mitral annular dilation and leaflet traction. This causes a failure of coaptation of the otherwise intact leaflets of the mitral valve, leading to regurgitation through a central orifice between the mal-coapting leaflet tips. Functional mitral regurgitation contributes to heart failure symptoms.

Annular and/or ventricular restraint are investigational mechanical approaches to mitigate symptoms of cardiac dysfunction, that may act by reducing heart failure manifestations during exertion and that may induce favorable “negative” chamber remodeling. Transcatheter Mitral Cerclage Annuloplasty is one such annular and/or ventricular restraint device strategy.

## 3.0 CLINICAL AND SCIENTIFIC JUSTIFICATION

There is precedent to support the safety of devices that reside in the coronary sinus to treat mitral valve regurgitation. But, these so-called ‘partial’ annuloplasty devices and approaches have had mixed results with regards to effectiveness. These shortcomings include compression in the commissural more than septal-lateral dimensions of the dilated annulus, compression of entrapped circumflex coronary arteries inducing myocardial ischemia or infarction predicted in up to two thirds of patient candidates, and compression applied far from the annulus when the individual patient coronary sinus anatomically runs along the far-left atrial wall. By contrast, cerclage imparts circumferential compression that reduces the septal-lateral dimension, incorporates a protection element to prevent extrinsic compression of

entrapped coronary arteries, and exhibit planar discordance that achieves annular reduction even when the coronary sinus is anatomically located along the posterior left atrial wall. Because it is an entirely right-sided procedure and device (i.e. it is not exposed to blood on the left side of the heart), we expect to have a similar safety profile to aforementioned partial annuloplasty devices.

Importantly, cerclage does not preclude other transcatheter mitral valve therapies in the future, including edge-to-edge mitral valve repair (e.g. Mitraclip), transcatheter mitral valve replacement (TMVR), or surgery. This stands in stark contrast with edge-to-edge repair, that is commonly performed outside the US for functional mitral regurgitation.

[figure not shown]
Two relevant randomized clinical trials have been published since this study was first proposed, both evaluating an alternative transcatheter treatment for functional mitral valve regurgitation.

The MITRA-FR was a randomized investigator-initiated comparison of Mitra-Clip leaflet apposition or medical therapy alone . At 12 months, the combined primary endpoint of death or unplanned hospitalization was 48.7% versus 47.4% for intervention versus control. The secondary endpoint of death was 24.3% versus 22.4% in the intervention and control groups respectively. This study did not support the use of *Mitra-Clip* therapy for functional mitral valve regurgitation.

#### 4.0 TREATMENT OPTIONS

Candidates for Transcatheter Mitral Cerclage Annuloplasty currently have limited treatment options: medical therapy (including cardiac resynchronization therapy) or open surgical mitral valve repair/replacement. Because open heart surgery is an invasive procedure, it is typically reserved for the patients who are highly symptomatic with severe mitral regurgitation and who have coronary artery disease that is likely to benefit from concomitant surgical revascularization. Most patients are therefore treated medically, and many will continue to experience heart failure-related symptoms, often leading to repeat hospitalizations. *MitraClip* is a recently approved option for functional mitral valve regurgitation, with inconsistent results in two recently reported randomized controlled clinical trials (see section 3.0 above).

## 5.0 STUDY DESIGN

### 5.1 OVERVIEW OF STUDY DESIGN

This is an early feasibility study (EFS) of the Transmural Systems Transcatheter Mitral Cerclage Annuloplasty device. It is a prospective, open-label, multi-center, investigator-initiated, and independently-adjudicated investigation of the cerclage device in patients with symptomatic functional mitral valve regurgitation due to underlying cardiomyopathy.

### 5.2 EVALUATION OF STUDY CANDIDATES AND PREPARATION FOR THE CERCLAGE PROCEDURE

Candidates will be identified by the participating structural heart disease programs. Imaging for procedural planning will include clinically-necessary imaging studies [specifically contrast-enhanced cardiac CT, transesophageal echocardiography (TEE), transthoracic echocardiography (TTE), cardiac catheterization and angiography, and if necessary cardiac magnetic resonance imaging (CMR)]. Candidates may authorize transmission of medical records and clinical imaging examinations using a protocol-specific screening form, if required by the enrolling site.

Eligibility will be reviewed and proposed by the local multidisciplinary heart teams. Anatomic eligibility will be confirmed by the echocardiography and CT analysis Core Laboratories. Candidates will then undergo central eligibility review by the Study Eligibility Committee. If deemed eligible, candidates will be offered participation in the study. Eligible subjects will be invited to sign the research consent only afterwards.

[figure not shown]
[figure not shown]
Candidates will be counseled about the importance of study compliance before enrollment. Once enrolled, subjects will undergo protocol baseline assessment. If eligible, subjects will be admitted to the hospital and undergo Transcatheter Mitral Cerclage Annuloplasty under this protocol. They will undergo follow-up testing including regular transthoracic echocardiography and CT scan before hospital discharge, 30 days, and 6 months.

Optionally, subjects may undergo baseline cardiopulmonary exercise testing (CPET), and/or stress (bicycle- or treadmill-) echocardiography, pending local site availability and subject willingness to participate.

### 5.3 TRANSCATHETER MITRAL CERCLAGE ANNULOPLASTY PROCEDURE

The Transcatheter Mitral Cerclage Annuloplasty procedure is planned from a time-resolved contrast-enhanced CT of the heart to confirm suitable coronary venous anatomy.

The final cerclage implant comprises two components, the cerclage implant with or without a coronary artery protection element, and the wishbone lock with coronary sinus and RVOT limbs.

If the subject is not undergoing therapeutic anticoagulation for another indication (such as atrial fibrillation), antiplatelet medication is administered on the day of the procedure (aspirin 162-325mg or clopidogrel or equivalent daily at the discretion of the treating physician).

The procedure is performed under general anesthesia or monitored anesthesia care at the discretion of the local heart team. The procedure is performed using fluoroscopy and echocardiography (typically transesophageal) guidance. The procedure is performed from a transjugular venous approach (preferably right side) with a single sheath. Femoral or radial arterial access is also required for selective left coronary angiography. After anticoagulation with heparin or equivalent to achieve activated clotting time (ACT) >250sec, a balloon wedge end-hole catheter is floated from the internal jugular sheath superior vena cava (SVC) to the pulmonary artery. Echocardiography and fluoroscopy are used to ensure the catheter does not undermine tricuspid valve chords or the right ventricle moderator band. A guidewire is used to exchange the balloon wedge end-hole catheter for the target capture catheter, which is then opened in the right ventricular outflow tract (RVOT). This serves as a target and as a snare to capture the septal traversal guidewire.

Using fluoroscopy, a balloon-tip guiding catheter is advanced from the same internal jugular sheath into the coronary sinus, the balloon is inflated and a coronary sinus venogram is acquired. Simultaneous selective left coronary angiography is acquired to confirm the anatomic relationship of the coronary sinus and the left circumflex artery. This serves to confirm the coronary venous anatomy identified on the pre-procedural CT scan. Coronary guidewires and coronary microcatheters are then used to navigate into a suitable coronary vein towards the target capture catheter.

Once the guidewire is confirmed through the open target capture catheter, the snare is closed to capture the guidewire tip. The target capture catheter is then withdrawn from the internal jugular sheath. The coronary sinus guidewire is advanced in tandem with the withdrawal of the target capture catheter. This creates a wire loop from the internal jugular sheath, along the coronary sinus, through the basal septum into the RVOT, through the tricuspid annulus, and back out of the internal jugular sheath.

The cerclage implant is then attached to the back end of the guidewire and pulled through the internal jugular sheath, along the coronary sinus, through the basal septum, through the tricuspid valve, and back out of the internal jugular sheath. The cerclage coronary sinus limb is shortened using a scalpel if necessary. The position of the cerclage implant is adjusted so that the coronary protection element lies directly over any underlying branch of the left coronary artery (typically the left circumflex and/or obtuse marginal branch of the circumflex).

The wishbone lock is then advanced over the two limbs of the cerclage implant and the desired tension is titrated to the degree of mitral regurgitation using echocardiography guidance. Selective coronary angiography is performed to confirm there is no coronary compression. Once the desired tension has

been achieved, the wishbone lock is locked and the two limbs of the cerclage implant are cut with a cutter catheter.

Echocardiography assessment of the mitral annulus and mitral regurgitation is again performed, along with repeat selective coronary angiography. The internal jugular sheath is then removed, and the patient convalesces in the appropriate inpatient recovery unit.

Before discharge, transthoracic echocardiography is performed. Repeat time-resolved cardiac CT is acquired if renal function allows, otherwise it is deferred to the 30-day follow up visit. If renal function does not allow contrast by the 30-day follow-up, non-contrast CT is performed for limited geometric assessment.

Anti-platelet medication is continued for 6 months, or longer at the discretion of the attending physician; anti-platelet medication is not required if the patient receives therapeutic anticoagulation.

Optionally, subjects may undergo follow-up cardiopulmonary exercise testing (CPEX), and/or stress (bicycle- or treadmill-) echocardiography, as outlined in section 5.4.

The procedure is unchanged in the presence of prior *Mitra-Clip*.

### 5.3.1 Pregnancy contingency

Should a subject become pregnant during the study, CT scans will be omitted but all other study-specific follow-up will be unaffected.

## 5.4 TIME AND EVENTS SCHEDULE

|   | Screening ± 6 wks     | Baseline ± 6 wks      | Day 0       | Inpatient | 30 d (±14d) FU | 2 yrs (± 1 mo) (range) | 12 mo (± 1 mo) (range) FU | 3 yrs (± 1 mo) | 5 yrs (± 1 mo) | 4 yrs (± 1 mo) |
|---|-----------------------|-----------------------|-------------|-----------|----------------|------------------------|---------------------------|----------------|----------------|----------------|
| Research informed consent   |                       | X                     |             |           |                |                        |                           |                |                |                |
| Multidisciplinary heart team eligibility determination                          | X                     |                       |             |           |                |                        |                           |                |                |                |
| Baseline clinical assessment  |                       | X                     |             |           |                |                        |                           |                |                |                |
| 6 minute walk test  |                       | X                     |             |           | X X X          |                        |                           |                |                |                |
| Kansas City Cardiomyopathy Questionnaire (KCCQ)-23                              |                       | X                     |             |           | X X X          |                        |                           |                |                |                |
| NYHA Classification   |                       | X                     |             |           | X X X          |                        |                           |                |                |                |
| Frailty tests: Katz ADL, 5MW, Albumin   |                       | X                     |             |           |                |                        |                           |                |                |                |
| Blood test for pregnancy (hCG)  | X                     | X                     |             |           |                |                        |                           |                |                |                |
| Blood tests (see below)   |                       | X                     |             | X         | X X X          |                        |                           |                |                |                |
| Vital signs and in-person visit   |                       | X                     |             |           | X X X          |                        |                           |                |                |                |
| Cardiac CT contrast-enhanced gated dynamic (Baseline may be up to 6 months old) | Screening or baseline | Screening or baseline | Inpatient * | 30-90d*   | X X            |                        |                           |                |                |                |
| Transesophageal echocardiogram. May be omitted day 0 with SEC concurrence       | Screening or baseline | Screening or baseline | X           |           |                |                        |                           |                |                |                |
| Transcatheter Mitral Cerclage Annuloplasty                                      |                       |                       | X           |           |                |                        |                           |                |                |                |
| Transthoracic echocardiogram (TTE). Baseline may be up to 3 months old.         | Screening or baseline | Screening or baseline |             | X X X X X |                |                        |                           |                |                |                |
| ECG   |                       | X                     |             | X X X X X |                |                        |                           |                |                |                |
| Adverse event assessment  |                       |                       | X X         | X X X X X |                |                        |                           |                |                |                |

|  | Screening ± 6 wks | Baseline ± 6 wks | Day 0 | Inpatient | 30 d (±14d) FU | 6 mo (± 1 mo) (range) FU | 12 mo (± 1 mo) (range) FU | 2 yrs (± 1 mo) (range) | 3 yrs (± 1 mo) | 4 yrs (± 1 mo) | 5 yrs (± 1 mo) |
|--|-------------------|------------------|-------|-----------|----------------|--------------------------|---------------------------|------------------------|----------------|----------------|----------------|
| Vital status, assessment of SAE and SADE, & clinical echo or echo report. Phone call and review of records from primary physician are acceptable |                   |                  |       |           |                |                          |                           | X                      | X              | X              | X              |
| OPTIONAL: Exercise echocardiogram  |                   |                  | X     |           | X              | X                        | X                         |                        |                |                |                |
| OPTIONAL: Cardiopulmonary Exercise Test (CPEx)   |                   |                  | X     |           | X              | X                        | X                         |                        |                |                |                |

\* follow-up contrast-CT scans may be postponed or omitted as required by patient renal function in written coordination with the sponsor representative.

Subjects would receive continuing care from their primary physicians with consultant input as requested from the structural heart disease program.

For subjects who die, necropsy evaluation is requested to examine the heart at NIH.

In Amendment C, an additional follow-up CT was added at 30-90 days.

In Amendment F, additional 6MWT, KCCQ, and proBNP tests were added at 6 months.

In Amendment G, assessment of and reporting of SAE and SADE is required for long term follow-up.

#### 5.4.1 Blood tests

All of the blood tests specified here are mandatory for routine medical care before, during, and after transcatheter mitral valve repair procedure. The results are recorded as research values and in surveillance for adverse events. **No other blood tests are reported as adverse events.**

The specific blood tests are enumerated below, and reported as study adverse events if change from baseline > 10% AND out-of-range:

| Test   | Detail  | Inpatient value to record | Timepoints to collect   |
|--|---|---------------------------|-------------------------|
| Blood count: hemoglobin                                  | Marker of anemia and hemodilution.  | Lowest                    | Baseline through 30d    |
| Blood count: hematocrit                                  | Marker of anemia and hemodilution.  | Lowest                    | Baseline through 30d    |
| Blood count: white blood cell count                      | Nonspecific marker of inflammation and infection.   | Highest                   | All except 6 mo         |
| Blood count: platelet                                    | Nonspecific marker of coagulation and of inflammation.                                    | Lowest                    | Baseline through 30d    |
| Chemistry: Albumin                                       | Marker of nutritional status and frailty  |                           | Baseline only           |
| Chemistry: Creatinine                                    | Marker of renal excretion.  | Highest                   | All                     |
| Chemistry: Estimated glomerular filtration rate (eGFR)   | Calculated from age, sex, race, and creatinine  | Lowest                    | All                     |
| Chemistry: NT-Pro-Brain natriuretic peptide (NT-Pro-BNP) | Marker of volume overload.  | Lowest                    | All                     |
| Chemistry: Cardiac troponin                              | Marker of cardiomyocyte injury, institution-specific subtype (Troponin-I or Troponin-T).  | Highest                   | Baseline through 30 day |
| Chemistry: Bilirubin, total                              | Used to classify Childs-Pugh status, collected only if available from clinical evaluation | Highest                   | Baseline only           |

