#### **10.0 ADVERSE EVENT REPORTING**

##### **10.1 DEFINITIONS**

*Adverse events:* Any untoward medical occurrence in a human subject, including any abnormal sign (e.g., abnormal physical exam or laboratory finding), symptom, or disease, temporally associated with the subject's participation in the research, whether or not considered related to the subject's participation in the research.

This will include:

- Expected events related to the subject's disease process during active enrollment in the research protocol and do not directly result from use of the investigational device or study.
- Procedural events directly related to the cardiac catheterization procedure and recovery from the procedure and do not directly result from use of the investigational device.

*Serious Adverse Event (SAE):* A serious adverse event that results in any of the following and NOT directly related to the device. This includes any event that

- Results in death
- Is life-threatening (places the subject at immediate risk of death from the event as it occurs);
- results in in-patient hospitalization or prolongation of existing hospitalization;
- results in a persistent or significant incapacity;
- results in a congenital anomaly/birth defect (not relevant to this study); or
- based upon appropriate medical judgment, may jeopardize the subject's health and may require medical or surgical intervention to prevent one of the other outcomes listed in this definition.

*Adverse Device Effect (ADE):* Any untoward or unintended response to a medical device. This definition includes any event resulting from insufficiencies or inadequacies in the instructions for use or the deployment of the device or any event that is a result of user error.

During this clinical investigation an event should be considered related to the device when it is the result of:

- Transcatheter Mitral Cerclage Annuloplasty procedure
- Transcatheter Mitral Cerclage Annuloplasty device

An event will be considered NOT related to the Transcatheter Mitral Cerclage Annuloplasty procedure when it is the result of a pre-existing medical condition.

*Anticipated Adverse Device Effects (AADEs):* An AADE is an adverse event with a reasonable possibility that the device or procedure caused or contributed to the event. The following AADEs are considered anticipated based on judgement and clinical experience:

- Death

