- Mechanical injury to the myocardium or heart valves that may cause elevation of myocardial biomarkers (Troponin) other than myocardial infarction
- Mechanical injury to, or decline in function of, tricuspid or aortic heart valves or subvalvular apparatus causing valve regurgitation including requiring mechanical intervention
- Chest pain
- Cardiogenic shock or hypotension caused by valvular, subvalvular, or myocardial injury during or after cerclage implantation procedure requiring vasopressor support or mechanical circulatory support or other mechanical or surgical intervention

- Myocardial erosion which may cause myocardial perforation, intracardiac shunt, pericardial effusion or tamponade and which may require surgical or transcatheter intervention
- Renal injury or failure, including contrast-induced nephropathy, requiring temporary or permanent hemodialysis or medical treatment
- Volume overload, congestive heart failure, dyspnea, pulmonary edema, or pleural or pericardial effusion from procedure-related volume perturbations
- Congestive heart failure, cardiomyopathy, cardiogenic shock, respiratory failure, BNP elevation
- Narrowing the mitral valve too much, causing a condition called mitral valve stenosis. This can result in lung congestion causing shortness of breath, similar to symptoms of leaky (regurgitant) mitral valve.
- Respiratory failure requiring oxygen or mechanical support or mechanical ventilation
- Endocarditis or endarteritis or sepsis related to the cerclage device
- Venous thrombosis or thromboembolism including deep vein thrombosis, and pulmonary thromboembolism
- Ecchymoses or gastric bleeding related to anti-platelet medications.
- Other infection related to access site or procedure including urinary or pulmonary or sepsis
- Pain including back pain and access site pain and generalized pain
- Low or high blood pressure values, or low or high heart rate values, whether related to anesthesia or not
- Abnormal blood cell tests including hemoglobin, hematocrit, platelets and white blood cells
- Abnormal blood chemistries including creatinine, troponin, and NT-pro-BNP
- Radiation injury including intractable skin injury
- Emergency cardiovascular surgery

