### **10.2.3 Adverse Event Reporting**

Adverse event recording will start on Day (0) of the Transcatheter Mitral Cerclage Annuloplasty procedure and will continue through the 12 month Follow Up. Assessment, recording and reporting of serious adverse events (SAE) and serious adverse device effects (SADE) will continue at annual visits thereafter.

New events or conditions present at baseline that increase in severity will be recorded and evaluated and reported on the case report form. Once the subject has completed the 30 day follow up, only serious adverse events (SAE), serious adverse device effects (SADE), unanticipated device effects (UADE) and unanticipated problems (UP) will be reported to the Sponsor . It is the responsibility of the site Principal Investigator to report adverse events and adverse device effects to the IRB of record, to the study sponsor, and to other regulatory bodies according to their reporting requirements. Monitoring visits will be conducted by the Sponsor to review source documentation, and accuracy and completion of the adverse event case report forms.

Section 5.4.1 enumerates blood tests that are monitored for adverse events. No other blood test are reported as adverse events.

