#### **10.2.5 Interim reporting to FDA CDRH for Early Feasibility Study**

For each sequential cohort of 5 subjects, we will summarize and transmit the 30-day data to FDA CDRH.

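### The laboratory adverse-event trigger in section 5.4.1 has no direction, so as written it flags improvements in values that remain out of range and disagrees with sections 10.1 and 10.2.3

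*Combined protocol and SAP*

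**What the plan says.** Section 5.4.1 lists the blood tests that serve both as research values and as adverse-event surveillance. A listed test is "reported as study adverse events if change from baseline > 10% AND out-of-range", and "No other blood tests are reported as adverse events". The table has a column headed "Inpatient value to record", with the entry lowest or highest for each test. It has no column for adverse direction.

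Three other places bear on the point:

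- Section 10.1 defines an adverse event as "Any untoward medical occurrence in a human subject, including any abnormal sign (e.g., abnormal physical exam or laboratory finding), symptom, or disease". Its list of anticipated adverse device effects includes "Abnormal blood chemistries including creatinine, troponin, and NT-pro-BNP", without direction. A separate item in the same list names elevation of BNP.
- Section 10.2.3 states: "New events or conditions present at baseline that increase in severity will be recorded and evaluated and reported on the case report form". It then points back to the laboratory rule: "Section 5.4.1 enumerates blood tests that are monitored for adverse events".
- Section 10.2.5 states: "For each sequential cohort of 5 subjects, we will summarize and transmit the 30-day data to FDA CDRH".

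**The concern.** Subjects with heart failure can be expected to start the study with some values out of range. For them the out-of-range half of the trigger is often met already, and a change of more than 10% either way completes it. A subject whose congestion, renal function or anemia improves without normalizing then meets the same criterion as one who deteriorates.

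This is an open-label study of 30 treated subjects with no control group described, at up to 6 sites. Section 9.2 names adverse events among the outcomes to be related to phenotype. If one site follows 5.4.1 literally and another applies 10.1 and 10.2.3, their laboratory adverse-event counts mean different things and cannot be pooled cleanly.

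**Working it through.** The plan gives no figure to reproduce. The check applies the rule to example values and then compares the sections.

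**Inputs.** The trigger comes from 5.4.1. The documents give no example values or reference limits, so both are assumptions, in customary units: hemoglobin 12–17, platelets 150–400, eGFR at least 60, creatinine 0.6–1.3, NT-proBNP up to 300, white cells 4–11.

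**Formula.** Percent change = (follow-up − baseline) / baseline. For NT-proBNP 4000 to 3000: (3000 − 4000)/4000 = -25%. For hemoglobin 10.0 to 11.2: (11.2 − 10.0)/10.0 = +12%. Both follow-up values remain out of range, so both meet the trigger.

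**Six tests, one improving and one worsening change each.** All follow-up values are still out of range.

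| Test | Improving | Worsening |
|---|---|---|
| Hemoglobin | 9.0 to 10.2, +13.3% | 9.0 to 7.8, -13.3% |
| Platelets | 90 to 110, +22.2% | 90 to 75, -16.7% |
| eGFR | 30 to 38, +26.7% | 30 to 25, -16.7% |
| Creatinine | 2.0 to 1.6, -20.0% | 2.0 to 2.4, +20.0% |
| NT-proBNP | 4000 to 2000, -50.0% | 4000 to 5000, +25.0% |
| White cells | 16 to 13, -18.8% | 16 to 19, +18.8% |

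| Reading of the rule | Improving flagged | Worsening flagged |
|---|---|---|
| Absolute change over 10% | 6 of 6 | 6 of 6 |
| Signed change over +10% | 3 of 6 (hemoglobin, platelets, eGFR) | 3 of 6 (misses the same three tests) |
| Over 10% in the adverse direction | 0 of 6 | 6 of 6 |

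The signed reading does not rescue the sentence. It still flags some improvements and also loses real deterioration.

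**Does the table supply direction indirectly?** No. The lowest/highest column only selects which inpatient value is recorded. For hemoglobin, hematocrit, platelets, white cells, creatinine, eGFR and troponin it selects the adverse side, which screens out most inpatient improvements. For NT-proBNP, which the table describes as a marker of volume overload, it selects the lowest value, whereas 10.1 names BNP elevation as the adverse effect. At follow-up visits the column has no role.

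**Where is the exposure?** Hemoglobin, hematocrit, platelets and troponin are collected only through 30 days. Albumin and bilirubin are baseline only. Under 10.2.3, after the 30-day follow-up only SAE, SADE, UADE and UP go to the sponsor, although recording continues to 12 months. The exposure is therefore mainly inpatient NT-proBNP and the 30-day visit.

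**Reading the sections together.** Under 10.1 and 10.2.3 none of the six improvements is reportable, because none is untoward, new or an increase in severity. Under 5.4.1 alone all six are.

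**The case against.** The strongest reply is that the general rules already exclude improvements. A reader might infer from 5.4.1 that every such improvement must be reported. The protocol as a whole does not support that, because 10.1 requires an untoward occurrence and 10.2.3 limits baseline conditions to those that worsen. This stands, and it reduces the point to a conflict between sections. It does not remove the conflict: 5.4.1 is the specific numeric rule, 10.2.3 sends the reader back to it, and 10.1 itself gives an abnormal laboratory finding as an example and lists abnormal chemistries without direction.

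A reader might also try to count spurious events. Suppose all 30 subjects have a stable, out-of-range NT-proBNP with log-normal within-person variation, so that the SD of the log ratio is √(2·ln(1+CV²)). For CVs of 10%, 20% and 30%, the chance of a fall of more than 10% is 0.228, 0.353 and 0.400, or 6.8, 10.6 and 12.0 per 30 subjects at one visit. The documents give neither the CVs nor the proportion out of range. In the same model, rises of more than 10% number about 7.5, 11.0 and 12.3, and a directional rule would keep those. Such a count mostly shows how sensitive a 10% threshold is to noise. It does not measure the lack of direction.

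A reader might further infer that listing hemoglobin with hematocrit, and creatinine with eGFR, double counts events. No section states a per-test counting rule, so there is nothing there to correct.

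Finally, broad capture is defensible in an early feasibility study, and the values themselves are kept, so worsening remains visible. That argues for keeping a sensitive trigger but does not justify classing improvement as an adverse event.

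**Conclusion.** The point holds as an inconsistency worth correcting. The 5.4.1 trigger is undirected, taken alone it flags improvements in values that stay out of range, and it does not match 10.1 and 10.2.3.

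The consequence is modest. Technical success, procedural success and the 30-day mortality stopping rule do not use the trigger. Bleeding, acute kidney injury and myocardial infarction are separate exploratory endpoints. What can be affected is the descriptive count of laboratory adverse events and, if those counts are included, the 30-day summaries for each 5-subject cohort; 10.2.5 refers only to 30-day data. The 6-of-6 and 0-of-6 results are illustrative and rest on assumed values and limits. The textual finding does not depend on them.

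**What to change.** 1. Replace the trigger sentence in 5.4.1 with wording such as: *reported as an adverse event if the value moves further out of range by more than 10% from baseline, or newly goes out of range with a change of more than 10%, in the adverse direction shown for that test.*
2. Add an adverse-direction column. Hemoglobin, hematocrit, eGFR: fall. Creatinine, NT-proBNP, troponin: rise. Platelets and white cells: either direction when moving away from the normal range. One-sided entries for these last two would drop abnormal changes that 10.1 leaves undirected.
3. Reconcile the lowest-value inpatient entry for NT-proBNP with the BNP-elevation item in 10.1.
4. Have the investigators who classify events under 9.2 review laboratory events already recorded for direction, where stored values allow. For inpatient NT-proBNP this is limited, because only the lowest value is specified for recording and a rise during the stay may not be recoverable from it.

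The cost is one sentence, one table column, one reconciled entry and a short review of existing records. No new tests are needed.
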